4.2 POPULATIONS

4.2.1 Study population

Approximately 156 patients will be included in the study to get about 140 evaluable patients.

The source population in this study is female patients suffering from EBC and treated with adjuvant endocrine monotherapy for 2 years (up to 1 year and 9 months) to 3 years (up to 3 years and 6 months), who spontaneously visit a hospital from the EADV European task force, in European countries (including France, Greece, Italy and Spain). They will be invited to participate in the study, during the inclusion period. The study population is the source population meeting eligibility criteria listed hereafter during the inclusion period.

4.2.1.1 Inclusion criteria

Patients will be eligible for inclusion if they fulfill ALL The following criteria:

1. Female aged \geq 18 years at inclusion.
2. Histologically confirmed diagnosis of EBC, according to the WHO criteria (**Lakhani, 2012; Cardoso, 2019; Tan, 2020**) and the TNM classification, (**Teichgraeber, 2021**) at any time before inclusion.
3. Still being treated with adjuvant endocrine monotherapy, initiated 2 years (up to 1 year and 9 months) to 3 years (up to 3 years and 6 months) before the inclusion in the study.
4. Signed Informed Consent Form (ICF) or non-opposition, according to local regulations.

4.2.1.2 Exclusion criteria

Patients will not be eligible for inclusion if they fulfill ANY of the following criteria:

1. Patients not able to read, understand and complete Questionnaires in local language.
2. Patients with chronic dermatological conditions (treated or not) before initiating the adjuvant endocrine therapy that could interfere with the quality of life.
3. Patients with concomitant targeted therapies with adjuvant endocrine therapy such as CDK4/6 inhibitors or trastuzumab, and patients with ongoing treatment with neratinib..
4. Patients having relevant or severe comorbidities requiring complex therapeutic treatment.
5. Patient having a persistent post-chemotherapy alopecia (at least of grade 1).

4.2.2 Patient selection

4.2.2.1 Study centers

The target countries for study participation will include European countries such as France, Greece, Italy, and Spain.

4.2.2.2 Patient selection

- Study initiation, patient selection, and data abstraction are planned to start in 2024.
- All female patients ≥ 18 years old with early breast cancer who are treated with any adjuvant endocrine monotherapy for 2 years (up to 1 year and 9 months) to 3 years (up to 3 years and 6 months) before the inclusion date.
- After verification of the eligibility criteria, the investigator or qualified designee will inform the patient about:
 - The study objectives,
 - The possibility of refusing to participate without any prejudice to the relationship with the investigator and the patient's medical care,
 - Processing of personal data that will be collected during this study and the rights of access, opposition, and rectification to this data.

The patient will be provided with a written or electronic information sheet about the study prior to data abstraction from patient records and completion of the questionnaires. If the patient agrees to participate, she will be asked to provide their written informed consent or non-opposition to study participation to the investigator (depending on local regulations), which will be documented in the patient's medical file before data collection.

Data that will be collected upon study inclusion are detailed below:

- Patient demographics,
- History of early breast cancer stage and date of diagnosis,
- History of procedures and treatments before the initiation of the adjuvant endocrine therapy in monotherapy,
- History of the adjuvant endocrine therapy in monotherapy (date of initiation, type of treatment),

- History of dermatological toxicities from the beginning of current treatment to the time of inclusion,
- Ongoing dermatological toxicities,
- Dermatological care and sun protective behaviors,
- Quality of life questionnaires.

4.3 STUDY OUTCOMES

The outcomes of this real word observational study are purely descriptive. They aim to describe mainly the quality of life related to dermatological toxicities of female patients with early breast cancer under adjuvant endocrine therapy in monotherapy, and also the demographics and clinical characteristics at the time of inclusion.

4.3.1 Primary outcome

The primary outcome is the description of the quality-of-life data collected at the time of inclusion using the validated DLQI questionnaire. The DLQI consists of 10 questions concerning patients' perception of the impact of skin diseases on different aspects of their health-related quality of life over the last week, including symptoms, feelings, daily activities, leisure, work, school, personal relationships, and treatment.

The primary endpoint is the rate of patients with a DLQI score ≥ 6 . The DLQI is calculated by summing the score of each question resulting in a maximum of 30 and a minimum of 0. The higher the score, the more quality of life is impaired:

- 0 – 1 corresponds to no effect at all on patient's life,
- 2 – 5 corresponds to small effect on patient's life,
- 6 – 10 corresponds to moderate effect on patient's life,
- 11 – 20 corresponds to very large effect on patient's life,
- 21 – 30 corresponds to extremely large effect on patient's life.

4.3.2 Secondary outcomes

1. Quality of life data collected at the time of inclusion using the Skindex-16, Hairdex, and ItchyQoL questionnaires.

The Skindex-16 includes items distributed across three domains symptoms (items 1 to 4), emotions (items 5 to 11) and functioning (items 12 to 16) and are answered on a seven-point Likert scale (varying from 0-never bothered, to 6-always bothered), which represents the frequency with which the skin problem bothered the respondent during the past week. This is a 0-100 scale, higher the score, the more quality of life is impaired.

The Hairdex is a valuable tool for evaluating disease-specific QoL in patients with hair disorders. It consists of 48 questions across five sections: symptoms, functioning, emotions, self-confidence, and stigmatization. Each question is self-graded on a scale of 0-4, with a score of 4 indicating the most severe change from a patient's baseline quality of life.

The ItchyQoL is a questionnaire used to measure the QoL in patients with chronic pruritus. It is composed of 22 items regarding symptoms, functions, emotions and self-perception, and is currently under copyright protection. In addition to the total score, a subscore for "symptoms", "functioning" and "emotions" can also be calculated. Each item is rated on a 5-point scale, ranging from 1 = never to 5 = all the time.

2. Ongoing dermatological toxicities reported by investigator according to Common Terminology Criteria for Adverse Events (CTCAE) (version 5.0, November 2017):
 - a. Type of toxicity
 - b. Surface area involved (except for nails and oral dryness)
 - c. Start date
 - d. Clinical grading of the toxicity
3. Demographics, and clinical characteristics at the time of inclusion, including the following items:
 - a. Age, gender, weight, height
 - b. Menopausal status
 - c. Date of cancer diagnosis
 - d. Primary tumor location
 - e. T stage
 - f. Prior therapies for breast cancer (type, agent name, start date, stop date)

- g. Endocrine therapy (agent name, start date) for breast cancer
- h. Current dermatological care and sun-protective behaviors

4.3.3 Exploratory outcomes

History of dermatological toxicities from the beginning of current treatment to the time of inclusion, including:

- a. Type of dermatological toxicity
- b. Surface area (except for nails and oral dryness)
- c. Start date and end date
- d. Grade of the toxicity, if available
- e. Change in hormonal treatment (adaptation, interruption), if applicable

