STUDY OBJECTIVES	
Primary objective
 
To measure the quality of life related to dermatological toxicities, using Dermatology Life Quality Index (DLQI) questionnaire, in female patients with early breast cancer (defined according to World Health Organization [WHO] classification and the 8th edition of the American Joint Committee on Cancer tumor, node, metastasis [TNM] staging system) being treated with ongoing adjuvant endocrine therapy in monotherapy, initiated 2 years (up to 1 year and 9 months) to 3 years (up to 3 years and 6 months) before inclusion in the study.
 
Secondary objectives
 
Secondary objectives aim, in female patients with early breast cancer (EBC), being treated with ongoing adjuvant endocrine monotherapy initiated 2 years (up to 1 year and 9 months) to 3 years (up to 3 years and 6 months) before inclusion in the study, to describe:
 
 1. The dermatological quality, using Skindex-16, Hairdex, and ItchyQoL questionnaires. 2. The real-world dermatological toxicities present at inclusion. 3. The demographics characteristics, and the clinical characteristics. 
Exploratory objectives
 
To describe real-world dermatological toxicities, from the beginning of their endocrine therapy to the time of data collection, of female patients with EBC, being treated with ongoing adjuvant endocrine monotherapy initiated 2 years (up to 1 year and 9 months) to 3 years (up to 3 years and 6 months) before inclusion in the study.

STUDY OUTCOMES	
Primary outcome
 
Quality of life data collected at the time of inclusion using the validated DLQI questionnaire.
 
The primary endpoint is the rate of patients with a DLQI score ≥ 6. The DLQI is calculated by summing the score of each question resulting in a maximum of 30 and a minimum of 0. The higher the score, the more quality of life is impaired: 0 – 1 corresponds to no effect at all on patient's life; 2 – 5 corresponds to small effect on patient's life; 6 – 10 corresponds to moderate effect on patient's life; 11 – 20 corresponds to very large effect on patient's life; 21 – 30 corresponds to extremely large effect on patient's life.

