	
Secondary outcomes
 
 1. Quality of life data collected at the time of inclusion using the Skindex-16, Hairdex, and ItchyQoL questionnaires. 2. Ongoing dermatological toxicities reported by investigator according to Common Terminology Criteria for Adverse Events (CTCAE) (version 5.0, November 2017): 
 a. Type of toxicity b. Surface area involved (except for nails and oral dryness) c. Start date d. Clinical grading of the toxicity 3. Demographics, and clinical characteristics at the time of inclusion, including the following items: 
 a. Age, gender, weight, height b. Menopausal status c. Date of cancer diagnosis d. Primary tumor location e. T stage f. Prior therapies for breast cancer (type, agent name, start date, stop date) g. Endocrine therapy (agent name, start date) for breast cancer h. Current dermatological care and sun-protective behaviors 
Exploratory outcomes
 
History of dermatological toxicities from the beginning of current treatment to the time of inclusion:
 
 a. Type of dermatological toxicity b. Surface area (except for nails and oral dryness) c. Start date and end date d. Grade of the toxicity, if available
--	--

	
e. Change in hormonal treatment (adaptation, interruption), if applicable.

STUDY DESIGN	
European (including France, Greece, Italy, Spain), multicenter (from the EADV European Academy of Dermatology and Venereology - European Task Force “Dermatology for cancer patients”), real world observational, cross-sectional study, to describe the quality of life related to dermatological toxicities, in female patients with EBC, treated with ongoing adjuvant endocrine monotherapy initiated for 2 years (up to 1 year and 9 months) to 3 years (up to 3 years and 6 months) before inclusion in the study. This is a cross-sectional, non-interventional study in which physicians and patients will follow local clinical practice.
 
Patients will be asked to complete 4 questionnaires at the time of their inclusion. Medical history, demographics, clinical characteristics, dermatological toxicities from the beginning of their endocrine therapy to the time of data collection will be collected from their medical charts. As this is a transversal study, there will not be any follow-up, and no safety data will be collected.

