3.3 EXPLORATORY OBJECTIVES

To describe real-world dermatological toxicities, from the beginning of their endocrine therapy to the time of data collection, of female patients with EBC, being treated with ongoing adjuvant endocrine monotherapy initiated 2 years (up to 1 year and 9 months) to 3 years (up to 3 years and 6 months), before inclusion in the study.

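### Does starting the toxicity history at "current treatment" in some places, and at endocrine therapy in others, leave the look-back undefined?

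*Protocol*

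**What the plan says.** The start of the toxicity history is worded in two ways.

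- **Start of endocrine therapy.** The exploratory objective in the synopsis is "To describe real-world dermatological toxicities, from the beginning of their endocrine therapy to the time of data collection", and section 3.3 uses the same anchor. The study design text, in the synopsis and in section 4.1, says that "dermatological toxicities from the beginning of their endocrine therapy to the time of data collection will be collected from their medical charts".
- **Start of current treatment.** The exploratory outcome in the synopsis is "History of dermatological toxicities from the beginning of current treatment to the time of inclusion", and section 4.3.3 repeats it: "History of dermatological toxicities from the beginning of current treatment to the time of inclusion, including" the items listed there. The list of data collected at inclusion in section 4.2.2.2 uses the same words.

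The eligible population in section 4.2.2.2 is women "who are treated with any adjuvant endocrine monotherapy for 2 years" or longer, within the permitted window. That list also names "History of the adjuvant endocrine therapy in monotherapy (date of initiation, type of treatment") and, separately, "History of procedures and treatments before the initiation of the adjuvant endocrine therapy in monotherapy". Section 4.3.2, item 3(g), lists agent name and start date for endocrine therapy. Section 4.3.3, item (e), adds changes in hormonal treatment.

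**The concern.** The looser phrase stands where sites are likely to look. Section 4.4 refers to the study outcomes section for the key data items, and section 4.2.2.2 is the collection list itself. Eligibility does not require the same agent throughout, so a patient may have changed agent during the window.

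If a site took *current treatment* to mean the present agent, its look-back for such a patient would begin at the change. Toxicities on the earlier agent would go unrecorded, including any that prompted the change. The loss would not be random, and an analysis plan cannot recover what was never abstracted. Sites reading the phrase differently would supply histories of different length. The optional subgroup by type of endocrine therapy would also be blurred for patients who took two agents.

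**Working it through.** The protocol states no figure on this point, so the check is a comparison of texts with a short illustration.

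**1. How the protocol uses the term.**

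| Place | What it ties the treatment to |
|---|---|
| Synopsis, study rationale | Patients currently treated with adjuvant endocrine monotherapy, dated from its initiation |
| 4.2.1.1, criterion 3 | Still on adjuvant endocrine monotherapy, dated from its initiation |
| 4.10, selection bias | Target population currently treated with that monotherapy, dated from its initiation |
| 4.2.2.2, collection list | The endocrine therapy history comes just before the look-back items; other treatments are those given before that therapy began |
| 4.3.2, item 3(g) | Says agent name when an agent is meant |

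In each of these places the ongoing treatment is the therapy. None of them uses the word treatment for the agent of the moment.

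**2. Test against the stated look-back length.** Section 4.10 (memory bias) says events are collected over a period running from 1 year 9 months to 3 years 6 months.

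- Lower limit: 12 + 9 = 21 months.
- Upper limit: 36 + 6 = 42 months.

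This equals the eligibility window in criterion 3. Let T be the time on therapy and m the month of a change of agent. The agent-level look-back is T − m, which for m > 0 can fall below 21 months. With an assumed m = 12 it runs from 21 − 12 = 9 to 42 − 12 = 30 months. Only the therapy-level reading gives 21 to 42 months for every patient.

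**3. Test against item (e).** The outcome includes changes in hormonal treatment. A look-back that began at the latest change of agent would leave out the toxicity that led to it, which works against this item.

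**4. Size for one patient if the phrase were misread.** The share of the history lost is m / T. The values of m are assumptions; the protocol gives none.

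| Assumed change at month | T = 21 | T = 42 |
|---|---|---|
| 6 | 6/21 = 29% | 6/42 = 14% |
| 12 | 12/21 = 57% | 12/42 = 29% |
| No change | 0% | 0% |

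These figures describe a single hypothetical patient. A study-level figure would need the proportion who changed agent and the proportion of sites using the narrow reading. The protocol gives neither.

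**5. What depends on it.** Section 4.7.5 describes the history by type, and by type and grade. Section 4.3.4 makes subgroup analyses optional. The DLQI proportion (4.7.3) and the ongoing toxicities (4.7.4) are taken at inclusion and do not use the look-back.

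The two wordings also end differently, at data collection or at inclusion. Section 4.4 settles that by collecting data up to the date of inclusion.

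**The case for a change.** The strongest case for a change is that this wording governs chart abstraction, not analysis. Around nine centres in several countries abstract independently, and section 4.10 already warns that toxicity reporting varies between them. Toxicities that lead to a change of agent are of particular interest, since the study rationale mentions treatment adjustment and interruption. The background cites hair changes at 4.4% overall against a highest figure of 25% with tamoxifen in one phase II trial, so the agent may matter. The listed endocrine fields do not plainly show a sequence of agents, and replacing a phrase in three places would cost little.

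Part of this stands. The wordings do differ, the term has no formal definition, and harmonising it would do no harm.

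The rest is weaker. Harm needs both a patient who changed agent and a site that adopts the reading the protocol's other text disfavours; nothing in the protocol suggests that this has happened. The 4.4% and 25% compare a pooled incidence with the highest single-trial value, and do not show that any result here would move. How agents are recorded is a matter for the eCRF, which is not shown and may already allow repeat rows. The collection list asks for a history of the endocrine therapy, which leaves room for more than one agent. A call for stop dates for each agent, or for queries on patients already included, would rest on a form that cannot be inspected.

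**Conclusion.** The concern does not call for a change. *Current treatment* is a loose synonym for the adjuvant endocrine therapy, and the surrounding text makes the intended look-back clear: from the start of that therapy to inclusion, 21 to 42 months. If the document is revised for another reason, the phrase can be aligned with sections 3.3 and 4.1 as an editorial matter.

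The effect is zero for patients who kept one agent and cannot be computed for the study as a whole. Any effect would be confined to a descriptive exploratory outcome and an optional subgroup. The conclusion assumes that sites read the outcome together with the objective, the design text and the eligibility criteria. It also assumes that the eCRF, which was not available, does not impose the narrower reading.

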4.3.4 Subgroups of interest

The following subgroups described are of interest:

- Age repartition by class (< 35 years old, 35-50, 50-65, > 65 years old)
- Menopause status
- Therapeutical choice before the 2/3 years of adjuvant endocrine therapy (2 years up to 1 year and 9 months, to 3 years up to 3 years and 6 months).
 - Radiotherapy (yes / no)
 - Chemotherapy (yes / no), if yes, the information whether taxane was received or not will be collected
 - Adjuvant (yes/no)
 - Neoadjuvant (yes/no)
 - Target therapy (yes / no)
 - Type of adjuvant endocrine therapy

Analyses of primary, secondary, and exploratory outcomes may be performed for some or all of these subgroups, subject to pertinence and the number of patients in each subgroup.

4.4 DATA SOURCES

Data for each patient will be collected until the date of inclusion. Questionnaires will be filled by patients at the time of their inclusion and data will be collected in their medical records during data abstraction period.

The source of collected data will include all elements that constitute a reliable source of patient-level information and are available at the center.

This includes inpatient medical charts (*e.g.*, consultation notes, discharge summaries, laboratory test results, recorded prescription data and any other documentation of communication with other health care providers). The center investigator will be responsible for ensuring that all the required data is collected and entered into an electronic Case Report Form (eCRF). The pseudonymization of entered data will be guaranteed by the use of a Subject Identifier. This pseudonymization will be maintained in the database used for statistical analysis.

Electronic Patient Reported Outcome (ePRO) will be used to collect questionnaires. Patients will be asked to fill questionnaires on site using tablets specifically dedicated to the present study.

Key data items that will be collected are listed in section Study outcomes.

4.5 STUDY SIZE

Within this study, it is planned to recruit 156 patients.

Accrual of 140 evaluable patients permits to estimate a 95% confidence interval of a proportion equals to 40% with an accuracy of +/-8%. The following table presents the accuracy for different proportions:

	Proportion of DLQI score ≥ 6			
	10%	20%	30%	40%
Accuracy (%)	+/-5	+/-6.5	+/-7.5	+/-8

Assuming a rate of around 10% of non-evaluable patients (missing data), 156 patients will be included to reach 140 evaluable patients.

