4.7 DATA ANALYSIS

4.7.1 General considerations

Statistical analyses will be fully described in a Statistical Analysis Plan (SAP). Analyses will be conducted with SAS® software, version 9.4 or higher.

Analyses will be descriptive in nature, as no hypothesis will be tested.

Demographic and clinical characteristics will be presented in the overall population using usual statistics. Quantitative data will be summarized as median, min, max and number of missing data. Qualitative variables will be described as number, percentage and number of missing data.

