4.7.3 Analysis of primary outcomes

The primary endpoint is the rate of patients with a DLQI score ≥ 6 . It will be described as number and percentage with corresponding 95% interval (binomial exact).

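### The accuracies given for 140 evaluable patients are not those of the exact binomial interval planned for the primary endpoint; the exact half-widths are 0.3 to 0.4 points larger

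*Protocol*

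**What the plan says.** Section 4.5 sizes the study on the precision of one proportion, the share of patients with a DLQI score of 6 or more. It says: "Accrual of 140 evaluable patients permits to estimate a 95% confidence interval of a proportion equals to 40% with an accuracy of +/-8" per cent. It continues "The following table presents the accuracy for different proportions", and lists ±5, ±6.5, ±7.5 and ±8 points at 10, 20, 30 and 40%. The synopsis carries the same sentence and table. Neither place names the interval method behind the figures.

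The recruitment target follows from this: "Assuming a rate of around 10% of non-evaluable patients (missing data), 156 patients will be included to reach 140 evaluable patients".

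Section 4.7.3 then sets the analysis of the same endpoint: "It will be described as number and percentage with corresponding 95% interval (binomial exact"). Section 4.7.1 adds: "Analyses will be descriptive in nature, as no hypothesis will be tested".

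**The concern.** The sizing table and the planned analysis concern the same quantity, so the table should show the precision that the planned interval will have. An exact (Clopper-Pearson) interval is wider than the usual approximate intervals at this sample size, and it is not symmetric about the estimate. Whole and half-point figures with a plus-or-minus sign suggest that an approximate formula was used instead.

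With no hypothesis test, this table is the whole case for 140 evaluable patients. If it describes a different interval, the protocol promises a precision that its own analysis will not deliver at that number, and the reported interval will come out wider than planned.

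**Working it through.** **Inputs.** n = 140 evaluable patients, two-sided 95% confidence, proportions of 10, 20, 30 and 40%, and stated accuracies of 5, 6.5, 7.5 and 8 points (section 4.5); exact binomial method (section 4.7.3). The corresponding counts are x = 14, 28, 42 and 56.

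**Step 1: reproduce the stated row.** The Wald half-width is 1.96 × √(p(1 − p)/140). At 40% this is 1.96 × √(0.24/140) = 8.12 points. The four values are 4.97, 6.63, 7.59 and 8.12. To the nearest half point they read 5, 6.5, 7.5 and 8, which is the stated row. Wilson half-widths (5.02, 6.59, 7.51, 8.01) round to the same row, so the method actually used cannot be identified.

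**Step 2: the interval fixed in section 4.7.3.** The Clopper-Pearson lower limit is the 0.025 quantile of Beta(x, n − x + 1). The upper limit is the 0.975 quantile of Beta(x + 1, n − x). The half-width is (upper − lower)/2. At 40%: (48.61 − 31.82)/2 = 8.40.

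| Proportion | Exact 95% limits (%) | Exact half-width | Stated | Excess | Exact, to nearest 0.5 |
|---|---|---|---|---|---|
| 10% (14/140) | 5.58–16.21 | 5.32 | 5 | 0.32 | 5.5 |
| 20% (28/140) | 13.72–27.59 | 6.94 | 6.5 | 0.44 | 7 |
| 30% (42/140) | 22.55–38.32 | 7.88 | 7.5 | 0.38 | 8 |
| 40% (56/140) | 31.82–48.61 | 8.40 | 8 | 0.40 | 8.5 |

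**Step 3: split the excess into method and rounding.** Exact minus unrounded Wald is 0.35, 0.31, 0.29 and 0.28 points. Unrounded Wald minus the stated figure is −0.03, 0.13, 0.09 and 0.12 points. Most of the gap is therefore the method.

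**Step 4: the two arms.** From the estimate to the upper limit the distances are 6.2, 7.6, 8.3 and 8.6 points, which exceed the stated figures by 1.2, 1.1, 0.8 and 0.6. To the lower limit they are 4.4, 6.3, 7.4 and 8.2, which exceed the stated figure only at 40%, by 0.2.

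**Step 5: the n that would support the row.** Here x = p × n is used in the beta quantiles without rounding.

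- Exact half-width below the stated figure plus 0.25, so that it rounds to the stated half point: n = 144, 148, 145 and 145. All four columns round to the stated row together from n = 148 (5.16, 6.74, 7.66, 8.16).
- Exact half-width no larger than the stated figure taken literally: n = 158, 159, 155 and 154.

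The recruitment figure itself is correct: 140/0.90 = 155.6, rounded up to 156.

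**The case against.** The strongest reply is that nothing turns on this. No hypothesis is tested, no required precision is set, and the reported interval will be exact whatever the planning table says. Planning with an approximate formula and reporting an exact interval is common practice, and the table is a correct calculation by an unnamed method. This stands as a limit on the importance of the point. It does not make the row true of the interval that section 4.7.3 prescribes.

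A second reply concerns rounding. The protocol states no rounding rule, and the 10% and 40% entries are printed as whole numbers. To the nearest whole point, 5.32 reads 5 and 8.40 reads 8, so only the 20% and 30% columns would fail. That is fair as far as it goes. But the entries 6.5 and 7.5 show that the row is kept to half points, and on that scale all four miss in the favourable direction.

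Third, up to 156 patients are recruited and the tablets use mandatory fields, so more than 140 may be evaluable. With all 156 evaluable, the exact half-widths would be 5.02, 6.56, 7.46 and 7.94, close to the stated row. That softens the practical consequence, but the sentence and the table are about 140.

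Finally, the larger excess in the upper arms comes largely from the asymmetry of the exact interval, which no single plus-or-minus figure can show. It should not be counted as a further error. It is a reason to print limits instead of half-widths.

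**Conclusion.** The concern holds. At 140 evaluable patients the planned exact interval has half-widths of 5.3, 6.9, 7.9 and 8.4 points, not 5, 6.5, 7.5 and 8. The understatement is 0.3 to 0.4 points, of which about 0.3 comes from the method.

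The comparison takes the exact binomial interval to be Clopper-Pearson. The finding that all four columns are too favourable after rounding, and the figure of 144 to 148 patients, assume the half-point rounding inferred from the table. The finding that the row is not the exact interval at n = 140 does not depend on identifying the formula that was used.

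The consequence is minor and gives no reason to change the sample size. It is still worth correcting, because the table is the sole stated justification for that size.

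**What to change.** In section 4.5 and in the statistics part of the synopsis, replace the ±8% sentence and the accuracy table with the exact binomial 95% limits at n = 140, labelled as the method of section 4.7.3:

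| Proportion | Exact binomial 95% limits, n = 140 |
|---|---|
| 10% | 5.6–16.2% |
| 20% | 13.7–27.6% |
| 30% | 22.6–38.3% |
| 40% | 31.8–48.6% |

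Keep the 140 evaluable patients, the 156 recruited and the analysis in section 4.7.3. The cost is a wording change in two places and slightly less favourable printed figures; no patients are added.
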